6.1. General Considerations

Statistical analysis of this study will be the responsibility of Eli Lilly and Company (hereafter Lilly). Any change to the data analysis methods described in the protocol will require an amendment ONLY if it changes a principal feature of the protocol. Any other change to the data analysis methods described in the protocol, and the justification for making the change, will be described in this SAP and/or in the clinical study report (CSR). Additional exploratory analyses will be conducted, as deemed appropriate.

Statistical analyses for Japan are described in [Appendix 2](#). Statistical Analyses for the Maximum Extended Enrollment (MEE) Addendum are described in [Appendix 3](#).

For purposes of analysis, the following populations are defined in [Table 6.1](#):

Table 6.1. Patient Populations

Population	Description
Entered	All patients who give informed consent.
Enrolled	All patients who receive at least 1 dose of open-label insulin lispro in the 8-week lead-in period.
Randomized	All patients who are randomly assigned to study treatment at Visit 8. Treatment group will be defined on the basis of the treatment the patients are assigned.
Safety	All randomized patients who receive at least 1 dose of the randomly assigned investigational product (IP). Treatment group will be defined on the basis of the treatment the patients are assigned.
Completer	Patients included in the randomized population who have completed Week 26 of study treatment without permanent discontinuation of IP. Treatment group will be defined on the basis of the treatment the patients are assigned.
Per Protocol	Patients included in the randomized population who have completed Week 26 of study treatment without permanent discontinuation of IP and without significant protocol deviations through Week 26 that would significantly impact the primary objective. Treatment group will be defined on the basis of the treatment the patients actually receive.

Unless otherwise stated, the efficacy analyses will be conducted on the Randomized Population, and the safety analyses will be conducted on the Safety Population.

The primary analysis is for the treatment period through Week 26.

Unless otherwise noted, all tests of treatment effects will be conducted at a 2-sided alpha level of 0.05, and CIs will be calculated at 95%, 2-sided. All tests of interactions between treatment groups and other factors will be conducted at a 2-sided alpha level of 0.10.

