The definitions of baseline and post-baseline for the efficacy and safety analyses depend on which analysis period is being used. The following analysis periods will be used:

- Lead-in Period – Visits 2 to 8
- 26-Week Treatment Period – from randomization to Week 26 prior to discontinuation of IP and from randomization to Week 26 (including all data regardless of IP use)
- 26-Week Treatment Period and Safety Follow-Up Visit – from randomization to Visit 801 (including all data regardless of IP use)

The data on IP is defined based on the following rules:

- For data only measured at an office visit
 - MMTT postbaseline data will be classified as on IP if the MMTT performance date is prior to or on the last IP dose date
 - Other postbaseline data (for example, vital signs, safety laboratory tests, and questionnaires) will be considered as on IP if the measurement was performed at or prior to the cutoff date defined as 14 days after the last IP dose date
- For data collected as running records with an exact date stamp such as adverse events (AEs) and diary entries where the dates of the measures were not tied with the date of an office visit, postbaseline data with dates \leq (last study drug dose date +1) will be considered as data on IP.

Table 6.2 describes the rules for determining the patient population, baseline and postbaseline observations for the different analysis periods.

For continuous measures, summary statistics will include sample size, mean, SD, median, minimum, and maximum for both the actual and the change from baseline measurements. Least-squares (LS) means and standard errors derived from the analysis models will also be displayed. Treatment comparisons will be displayed showing the treatment difference LS means and the 95% CIs for the treatment differences, along with the p-values for the treatment comparisons.

For categorical measures, summary statistics will include sample size, frequency, and percentages. Fisher's exact test or Pearson's chi-square test will be used for treatment comparisons.

For laboratory values, both conventional (CN) and Systeme International (SI) units will be presented. Therefore, both % and mmol/mol will be presented for HbA1c and both mg/dL and mmol/L will be presented for glucose measurements.

All baseline measures will be analyzed using an analysis of variance (ANOVA) model that has treatment as the model term.

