Study Period/Analysis	Patient Population	Baseline Observations	Post-Baseline Observations
1,5-AG	All Randomized Patients with a baseline and at least one post-baseline observation	Visit 8 prior to initiation of IP	Visits 11, 15, and 18 prior to discontinuation of IP AND Last of Visits 9-18 prior to discontinuation of IP
Health outcomes: ITSQ, EQ-5D-5L, EQ-VAS, WPAI-GH	All Randomized Patients with a baseline and a post-baseline observation	Last of Visits 1-8	Last of Visits 9-18 prior to discontinuation of IP
Safety Laboratory Tests (chemistry, hematology, lipids) – continuous analysis	All Patients in the Safety Population with a baseline and a post-baseline observation	Last of Visit 1-8	Visit 18 (planned) AND last of Visits 9-18 (planned including early discontinuation visits) regardless of IP use
Safety Laboratory Tests (chemistry, hematology, lipids) – categorical analysis	All Patients in the Safety Population with a normal baseline (with respect to the direction being analyzed) and a post-baseline observation	Visits 1-8 (including unplanned tests)	Visits 9-18 (including unplanned tests) regardless of IP use
TEAEs	All Patients in the Safety Population	Prior to first dose of randomized IP (or Visit 8 date if the dose date is missing) but after the first dose of open-label insulin lispro in the Lead-in Period	From first dose of randomized IP to last dose of randomized IP AND From first dose of randomized IP to Visit 801
Hypoglycemia events	Safety Population	All Visits 2-8	All Visits 9-18 prior to discontinuation of IP
Weight and vital signs	All Patients in the Safety Population with a baseline and a post-baseline observation	Last of Visits 2-8	Visits 9-18 prior to discontinuation of IP AND Visits 9-801 regardless of IP use
Anti-insulin lispro antibodies	Safety Population	Visit 2	Visits 3-801 regardless of IP use

Abbreviations: 1,5-AG = 1,5-Anhydroglucitol; ANCOVA = analysis of covariance; EQ-5D-5L = European Quality of Life - 5 Dimensions 5 Level; EQ-VAS = EuroQol visual analogue scale; HbA1c = hemoglobin A1c; IP = investigational product; ITSQ = Insulin Treatment Satisfaction Questionnaire; ITT = intention-to-treat; LOCF – last-observation-carried forward; MMTT = mixed meal tolerance test; MMRM = mixed-effect model repeated measures; PPG = postprandial glucose; SMBG = self-monitored blood glucose; TEAE = treatment-emergent adverse event; WPAI-GH = Work Productivity and Activity Impairment General Health.

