The number and percentage of patients with common TEAEs (defined as $\geq 5\%$ before rounding for LY900014-treated patients) will be summarized by treatment group using MedDRA PT (without regard to SOC). Events will be ordered by decreasing frequency. Treatment will be compared by Fisher's exact test.

The number and percentage of patients who experienced an SAE including deaths and SAEs temporally associated or preceding deaths will be summarized by treatment group using MedDRA PT regardless of SOC. Events will be ordered by decreasing frequency. A listing of all SAEs will also be provided.

The number and percentage of patients who discontinued from study due to an AE will be summarized by treatment group using MedDRA (without regard to SOC) using all data regardless of IP use. The number and percentage of patients who discontinued IP due to an AE will be also summarized by treatment group using MedDRA PT (without regard to SOC) using data prior to permanent discontinuation of IP. Events will be ordered by decreasing frequency. A listing of all AEs as reason for study or IP discontinuation will also be provided.

The number and percentage of patients who experienced other notable TEAEs (potential systemic hypersensitivity reaction, injection site reaction, and hepatic disorder) will be summarized by treatment group using all TEAEs regardless of IP use. For events that are gender-specific (as defined by MedDRA), the denominator and computation of the percentage will include only patients from the given gender.

Table 6.5 summarizes the planned analyses and the requirement of analysis data for different analysis periods. A 'Yes' in the IP USE column indicates that only data collected prior to permanent discontinuation of IP will be included.

Table 6.5. Treatment-Emergent Adverse Event Analysis Periods

Analysis Period	Analysis Population	Analysis	IP USE	Treatment
Lead-in Period	All enrolled patients	AE overview; TEAE by PT; SAE, discontinuation due to AE	N/A	Open-label insulin lispro
Treatment Period (0-26 Weeks)	All patients in safety population	AE overview; TEAE by SOC and by PT; common TEAE; TEAEs by maximum severity; SAE; IP discontinuation due to AE	Yes	LY900014, insulin lispro
Week 0 – Visit 801	All patients in safety population	AE overview; TEAE by SOC; common TEAE; SAE; other notable AEs; study discontinuation due to AE	All data regardless of IP use	LY900014, insulin lispro

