6.12.4.1. Hypoglycemic Events

Hypoglycemia events that occur during the study outside the MMTT will be captured using an eCOA diary starting from Visit 2 through Visit 801. Whenever hypoglycemia is suspected, the patient should record the blood glucose value, any associated symptoms, and the treatment administered in eCOA. A set of events is counted as 1 event in analysis if it consists of an originating event and subsequent continuing events as marked by the patient in eCOA, or the duration between adjacent events is ≤ 30 minutes. The event with the highest severity will be selected for analysis with severity determined in the order of: 1) it is a severe hypoglycemia, 2) it has symptoms of hypoglycemia reported, and 3) it has the lowest blood glucose value. If there are multiple events tied in all 3 aspects, the event with the largest number of non-missing responses to the questions of nocturnal hypoglycemia and postmeal time frame will be selected. If there are still multiple events tied, the latest event (based on data entry time) will be selected.

The following types of hypoglycemia events will be derived in the analysis data sets: documented hypoglycemia, severe hypoglycemia, nocturnal hypoglycemia, probable symptomatic hypoglycemia, and overall hypoglycemia. Only severe hypoglycemia will be collected as AEs and all episodes of severe hypoglycemia will be considered as SAEs. Documented hypoglycemia (including documented symptomatic hypoglycemia, documented asymptomatic hypoglycemia and documented unspecified hypoglycemia) will be based on blood glucose (BG) ≤ 70 mg/dL. In addition, documented clinically significant hypoglycemia with similar criterion as above documented hypoglycemia except for the threshold of BG < 54 mg/dL will be summarized.

Table 6.6 provides detailed statistical methods for each endpoint related to hypoglycemia. For these analyses, hypoglycemia events prior to the discontinuation of IP will be summarized.

Additional analyses for other types of hypoglycemic events not mentioned in the table and for the post-treatment period may be conducted as needed.

The incidence and number of episodes of hypoglycemia during the MMTT will be summarized by treatment and time relative to the meal (≤ 0.5 , ≤ 1 , ≤ 2 , ≤ 4 , >1 to ≤ 2 and >2 to ≤ 4 hours after start of the meal) and analyzed by Fisher's exact test.

A listing of patients with at least 1 severe hypoglycemia reported (as SAE) after randomization will be provided.

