A list of MedDRA PTs will be used for the narrow search of potential severe hypoglycemia in spontaneously reported AEs. The events identified through the search strategy that are also reported as SAEs will be summarized and compared between treatments. Fisher's exact test will be used to assess the treatment difference in the proportion of patients with potential severe hypoglycemia.

Table 6.6. Summary of Analyses for Endpoints Related to Hypoglycemia

Endpoint	Analysis Period	Statistical Method
Rate of hypoglycemic events (per patient per 30 days / year) 
 • All Documented^a • Nocturnal^a • Documented Symptomatic^a • Overall • Non-Nocturnal (Documented and occurred between waking and bedtime)^a • Probable Symptomatic 	0-4, 0-12, 0-26, 4-8, 8-12, 12-26 weeks	Negative binomial regression with treatment, and baseline hypoglycemia event rate with the same category of the dependent variable as covariates, log (exposure/30/365.25 days) as the offset in the model.
Incidence of hypoglycemic events 
 • All Documented^a • Nocturnal^a • Documented Symptomatic^a • Overall • Non-Nocturnal (Documented and occurred between waking and bedtime)^a • Probable Symptomatic 	0-4, 0-12, 0-26, 4-8, 8-12, 12-26 weeks	Logistic regression with treatment, baseline hypoglycemia event rate with the same category of the dependent variable as covariates.
Rate of postmeal hypoglycemic events (per patient per 30 days / year) for all 3 main meals 
 • Documented Symptomatic^a • Documented Asymptomatic^a 	≤ 0.5 , ≤ 1 , ≤ 2 , ≤ 4 , >1 to ≤ 2 and >2 to ≤ 4 hours after start of a meal within 0-12,12-26, 0-26 weeks	Negative binomial regression with treatment, baseline postmeal hypoglycemia event rate with the same category of the dependent variable as covariates, log (exposure/30/365.25 days) as the offset in the model.
Incidence of postmeal hypoglycemic events for all 3 main meals 
 • Documented Symptomatic^a • Documented Asymptomatic^a 	≤ 0.5 , ≤ 1 , ≤ 2 , ≤ 4 , >1 to ≤ 2 and >2 to ≤ 4 hours after start of a meal within 0-12,12-26, 0-26 weeks	Logistic regression with treatment, baseline postmeal hypoglycemia event rate with the same category of the dependent variable as covariates.

Summary of Analyses for Endpoints Related to Hypoglycemia

Endpoint	Analysis Period	Statistical Method

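### In the later hypoglycemia windows (4-8, 8-12 and 12-26 weeks), the SAP read literally keeps patients already off investigational product in the incidence denominator as forced non-events

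*SAP*

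**What the plan says.** **Population.** SAP Section 6.1 states that, unless otherwise specified, "the safety analyses will be conducted on the Safety Population". That population is every randomized patient with at least one IP dose; it carries no condition about being on IP at a later time. The hypoglycemia row of Table 6.2 names the Safety Population and adds nothing. Section 6.12.4 refers to Table 6.5, whose treatment-period row reads "All patients in safety population" with on-IP data.

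**Events counted.** The same row of Table 6.2 limits post-baseline observations to "All Visits 9-18 prior to discontinuation of IP". Section 6.12.4.1 repeats the rule for everything in Table 6.6: "For these analyses, hypoglycemia events prior to the discontinuation of IP will be summarized". For diary data, Section 6.1 ends the on-IP period one day after the last dose.

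**Windows and incidence model.** Table 6.6 lists "0-4, 0-12, 0-26, 4-8, 8-12, 12-26 weeks" in both the rate row and the incidence row for the main categories. For postmeal and severe events the windows are 0-12, 12-26 and 0-26 weeks. The incidence model for the main categories is "Logistic regression with treatment, baseline hypoglycemia event rate with the same category of the dependent variable as covariates", and the postmeal and severe rows are analogous. None has an exposure term or a rule on who is at risk in a window.

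**Rate model.** For non-severe and postmeal events, Table 6.6 uses negative binomial regression with a log-exposure offset. Protocol Section 10.3.4 makes clear that this is treatment exposure within the period analyzed.

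**The concern.** Take a patient who stops IP in Week 3. In the 12-26 week window no event in that patient can count, whether or not the patient remains in the study, because off-IP events are excluded by rule. The logistic model nevertheless records a non-event. That is a consequence of the counting rule, not an observation that the patient was free of hypoglycemia.

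The rate model for the same window cannot use this patient, because the log of zero exposure is undefined. Two results printed side by side for one window would then rest on different patients, and no visible text reconciles them.

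At stake is the reading of Weeks 12-26, the maintenance period after intensive titration, where this effect is largest. On-treatment incidence there would look lower than it is, and an arm with more early discontinuation would look safer for a reason unrelated to hypoglycemia risk on treatment.

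**Working it through.** The documents give no incidence figure to reproduce. The only relevant planned figure is attrition.

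**Inputs**
- Protocol Section 10.1: 670 randomized, 568 completing, 1:1 allocation, so 670/2 = 335 per arm.
- Planned non-completion: d = 1 - 568/670 = 15.2%. As a check, 568/0.85 = 668.2, or 669 rounded up, which agrees with the stated approximate 670.
- Assumptions not in the documents: IP discontinuation equals d and is linear over 26 weeks; on-treatment incidence pi in a window is 50%, with a range of 20% to 80%.

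**Share off IP when the window opens:** f(t) = d × t/26.

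**Incidence as reported under the literal reading:** pi × (1 - f).

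| Window starts | f | Patients per arm (335 × f) | Reported when pi = 50% |
|---|---|---|---|
| Week 4 | 15.2% × 4/26 = 2.3% | about 8 | 48.8% |
| Week 8 | 15.2% × 8/26 = 4.7% | about 16 | 47.7% |
| Week 12 | 15.2% × 12/26 = 7.0% | about 24 | 46.5% |

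A constant discontinuation hazard instead of a linear one gives 2.5%, 5.0% and 7.3%. For the 12-26 week window, true values of 20%, 60% and 80% would be reported as 18.6%, 55.8% and 74.4%.

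**Effect on the odds ratio**
- *Equal f in both arms, no true effect.* Both proportions shrink by the same factor, so the odds ratio stays 1.00.
- *Equal f, true effect.* The effect is diluted. At f = 7%, a true 60% versus 70% (odds ratio 1.56) becomes 55.8% versus 65.1% (odds ratio 1.48).
- *Unequal f, no true effect.* Assume 5% of one arm and 9% of the other are off IP by Week 12, with pi = 50% in both. The reported proportions are 0.50 × 0.95 = 0.475 and 0.50 × 0.91 = 0.455. The odds ratio is (0.455/0.545)/(0.475/0.525) = 0.92 and its log is -0.080. The unadjusted standard error is √[1/(335 × 0.475 × 0.525) + 1/(335 × 0.455 × 0.545)] = 0.155, so the shift is 0.080/0.155, about half a standard error.
- *Range over pi for the same 5% versus 9% split.* At pi = 20% the odds ratio is 0.95. At pi = 80% it is 0.85: log -0.168, standard error √[1/(335 × 0.76 × 0.24) + 1/(335 × 0.728 × 0.272)] = 0.177, a shift of just under one standard error.

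**Windows starting at randomization.** Every Safety Population patient takes at least one dose, so none is off IP before the 0-4, 0-12 or 0-26 week window opens: f = 0 and this mechanism does not operate. Those windows are touched only by partial exposure, which is a different matter.

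**The case against.** The strongest reply is that the SAP nowhere says off-IP patients count as event-free. Table 6.2 names a general population and restricts observations to those on IP; a patient with no on-IP time in a window has no qualifying observation there, so a programmer could reasonably leave that patient out. Part of SAP Section 6.3, on dropouts and missing data, is redacted and might hold a rule. It stands that the consequence is inferred and not stated. But the visible text does not contain the excluding reading. Table 6.2 writes narrower denominators into other rows when it wants them (HbA1c requires an on-IP post-baseline value; categorical laboratory analyses require a normal baseline) and leaves this row without one.

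A second reply is that the literal version is a legitimate quantity: the proportion of treated patients with an on-treatment event in the window, as in the adverse event tables. That is fair. The incidence is understated only if it is read as risk while on treatment. The rate beside it in Table 6.6 is read that way.

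Third, the plan already offers safeguards: exposure-adjusted rates for each window, a between-arm comparison of time to treatment discontinuation (Section 6.6) and a summary of exposure (Section 6.12.1). An imbalance large enough to matter would be visible. This lowers the priority but does not remove the mismatch.

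Fourth, restricting the denominator conditions on staying on IP, an outcome after randomization. If hypoglycemia itself leads patients to stop, the later-window comparison is between selected patients. This objection stands and belongs in the SAP text with the fix.

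**Conclusion.** The point holds as a gap in the specification of supportive analyses. Followed literally, Tables 6.2, 6.5 and 6.6 understate on-treatment incidence in the later windows by a relative 2%, 5% and 7% for windows opening at Weeks 4, 8 and 12, and the non-severe and postmeal rate models for the same windows leave out the patients responsible. These sizes rest on IP discontinuation matching planned non-completion and being linear.

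Two stronger conclusions might be inferred and are not supported:
- *That the listed hypoglycemia incidence endpoints are biased by this.* Objectives 6 and 7 run from baseline through Week 26, so this mechanism does not reach them. The affected windows are supplementary, and SAP Section 6.5 makes no multiplicity adjustment for these objectives.
- *That the treatment comparison is generally biased.* With no true effect, the odds ratio moves only if early IP discontinuation differs by arm. The documents give no reason to expect that in a double-blind trial with insulin lispro in both arms, and the 5% versus 9% split is an assumption. Even then the shift is about half a standard error at 50% incidence.

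It is worth correcting because the repair is small and makes rate and incidence comparable. It does not threaten the trial's main conclusions.

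**What to change.** Add to SAP Table 6.6 that, for each incidence window starting after Week 0, the denominator is Safety Population patients with on-IP exposure greater than zero in that window, the same set the rate model can use, and that this number is shown by arm. Apply it to the 4-8, 8-12 and 12-26 week rows for the main categories and to the 12-26 week rows for postmeal and severe events. Carry it into the hypoglycemia subgroup analyses of Section 6.13.2, which reuse these models, wherever a later window is used.

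Add a note that these comparisons are conditional on remaining on IP, and that partial exposure within a window is handled by the exposure-adjusted rate, not by the incidence model. A patient with one on-IP day in the window still enters the incidence as a full observation.

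The cost is a sentence or two in the SAP and one programming filter. Denominators in the later windows fall by roughly 8, 16 and 24 patients per arm under the assumptions above. Windows starting at Week 0 are unchanged.
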